5.1.1.3 Primary Immunogenicity Hypotheses

No hypotheses will be tested.

5.1.1.4 Statistical Methods for Primary Immunogenicity Objective

The primary endpoints for the evaluation of immunogenicity are based on neutralizing antibody titers, which will be measured with the neutralization assay. The statistical analyses will be performed for the following primary endpoints below on overall population and by age group:

1. Antibody titer on D01, D22, and D36
2. Fold-rise (fold-rise in serum antibody neutralization titer post-vaccination relative to D01) at D22, and D36
3. 2-fold and 4-fold rise in serum neutralization titer relative to D01 at D22, and D36
4. Occurrence of neutralizing antibody seroconversion, defined as baseline values below LLOQ with detectable neutralization titer above assay LLOQ at D22 and D36.

Vaccine arms will be aggregated to perform complementary assessments on the following main effects. The primary endpoints above will also be summarized for the main effects.

1. age [(18-49 years, \geq 50 years), where the category of 18-49 years (N=240) includes all vaccine arms except high dose no adjuvant arm aged 18-49 years old; the category of \geq 50 years (N=120) includes all vaccine arms aged 18-49 years old.]
2. dose (low, high), where the category of low (N=180) includes vaccine arms of low dose with either AF03 or AS03 adjuvant; the category of high (N=180) includes vaccine arms of high dose with either AF03 or AS03 adjuvant.
3. injection schedule (1-injection, 2-injection), where the category of 1-injection (N=120) includes vaccine arms in cohort 1; the category of 2-injection (N=240) includes vaccine arms in cohort 2 except the high-dose with no adjuvant arm.

4. adjuvant type (AS03, AF03), where the category of AS03 (N=240) includes vaccine arms with adjuvant AS03; the category of AF03 (N=120) includes vaccine arms with adjuvant AF03.
5. overall adjuvant (high-dose with adjuvants, high-dose without adjuvants), where the category of high-dose with adjuvants (N=180) includes vaccine arms of high-dose with either AS03 or AF03; the category of high-dose without adjuvants (N=20) includes the vaccine arm with high-dose and no adjuvant.
6. dose-sparing adjuvant (low-dose with adjuvants, high-dose without adjuvants); where the category of low-dose with adjuvants (N=180) includes vaccine arms of low-dose with either AS03 or AF03; the category of high-dose without adjuvants (N=20) includes the vaccine arm with high-dose and no adjuvant.

Additionally, to evaluate independent determinants of primary immunogenicity endpoints, regression models may be constructed for GMT titers and occurrence of 4-fold rise in serum neutralization titer relative to D01 at D22 for cohort 1 and D36 for cohort 2. When the outcome/dependent variable is a continuous numerical variable, linear models may be utilized; when the outcome/dependent variable is a categorical variable, logistic regression models may be utilized. Explanatory/independent variables inserted in these models would include age group (18-49 years, ≥ 50 years), antigen dose level (low-dose, high-dose), and adjuvant (none, AS03, AF03). Models evaluating antibody titers or rates at D22 for cohort 1 and D36 for cohort 2 as the outcome variable would include also an explanatory variable corresponding to the injection schedule (1-injection, 2-injections). Multiplicative interaction terms will be included in expanded models to assess for evidence of effect modification. Non-significant interaction terms with critical value < 0.05 can be removed from the models.

For descriptive purposes, the statistics presented on [Table 5.1](#) will be produced.

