9.1 Statistical Hypotheses

All analyses will be descriptive; no hypotheses are planned to be tested.

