9.2 Sample Size Determination

This is a first-in-human study to assess the safety profile and immune responses to different formulations of the study vaccine when compared to placebo. A total of 440 participants will be enrolled. No formal power calculation has been performed. The sample size was determined based on logistical considerations and common practices for first-in-human trials.

Vaccine arms will be aggregated to perform complementary assessments on the following main effects: age [(18-49 years [N=240], \geq 50 years [N=120]), dose (low [N=180], high [N=180]), injection schedule (1-injection [N=120], 2-injection [N=240]), adjuvant type (AS03 [N=240], AF03 [N=120]), overall adjuvant (high-dose with adjuvants [N=180], high-dose without adjuvants [N=20]), and dose-sparing adjuvant (low-dose with adjuvants [N=180], high-dose without adjuvants [N=20]).

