9.4.2 Primary Endpoints

9.4.2.1 Immunogenicity

The primary endpoints for the evaluation of immunogenicity are based on neutralizing antibody titers, which will be measured with the neutralization assay. The statistical analyses that will be performed for the following primary endpoints are as presented in [Table 3.1](#).

Pre-vaccination titers at < LLOQ will be converted to half LLOQ.

The 95% CIs for the GMTs/GMCs and GMT ratios will be calculated using normal approximation of log-transformed titers. The 95% CIs for the proportions will be based on the Clopper-Pearson method. The ratios of GMTs will be obtained between groups with the 95% CIs calculated using normal approximation of log-transformed titers. The differences in the seroconversion rates between groups will be computed along with the 2 sided 95% CIs by the Wilson-Score method without continuity correction. Additional parameters may be displayed as appropriate.

Additionally, to evaluate independent determinants of primary immunogenicity endpoints, regression models may be constructed for GMT titers and occurrence of neutralizing antibody seroconversion. When the outcome/dependent variable is a continuous numerical variable, linear models may be utilized; when the outcome/dependent variable is a categorical variable, logistic regression models may be utilized. Explanatory/independent variables inserted in these models would include age group (18-49 years, \geq 50 years), antigen dose level (low or high), and adjuvant (none, AS03, AF03). Models evaluating antibody titers or rates at D36 as the outcome variable would include also an explanatory variable corresponding to the injection schedule (1-injection, 2-injections). Multiplicative interaction terms will be included in expanded models to assess for evidence of effect modification. Non-significant interaction terms can be removed from the models.

Immunogenicity analyses will be performed on PPAS-IAS, unless otherwise specified.

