All participants will receive 1 injection of either one of the investigational study vaccine formulations or the placebo control at Day (D)01 (Vaccination [VAC] 1). Participants in Cohort 2 will receive a second injection of study vaccine formulation or placebo at D22 (VAC2). Participants are planned to be followed approximately 365 days post-last dose

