‡ Safety laboratory assessments will include: Serum Chemistries (liver enzymes / Chem 7, lipase, and amylase); hematology (complete blood count with differential); Urinalysis; Microscopy. In cases of abnormal safety laboratory results, unscheduled visits may occur, based on Investigator's judgment.

§ BL0001, MC0001, WB0001 and the first safety laboratory assessment sample will be collected at pre-VAC1 (baseline); and BL0002, MC0002, and WB0002 samples will be collected at pre-VAC2.

** Participants will use this DC1 to record information about solicited reactions, unsolicited AEs, SAEs, and AESIs from D01 to D08 after vaccination and will continue to record information about unsolicited AEs, SAEs, and AESIs from D09 to V02.

†† The Investigator or an authorized designee will remind the participants to bring back the DC at the next visit and will answer any questions.

‡‡ The Investigator or an authorized designee will interview the participants to collect the information recorded in the DC and will attempt to clarify anything that is incomplete or unclear.

§§ Participants will use this DC2 to record solicited reactions, unsolicited AEs, SAEs, and AESIs (from V02 to V03) and will continue to collect unsolicited AEs, SAEs, and AESIs (from V03 to V04).

*** Participants will use this DC3 for unsolicited AEs follow-up until D43 and SAEs, AESIs, and COVID-19-like illness follow-up from V04 to V05.

††† Participants will use this DC4 for SAEs, AESIs, and COVID-19-like illness follow-up from V05 to V06.

‡‡‡ Participants will use this DC5 for SAEs, AESIs, and COVID-19-like illness follow-up from V06 to V07.

§§§ During the D09 telephone call, staff will review the DC1 for solicited reactions from D01 to D08 after vaccination, inquire whether the participant experiences any SAE or AESI not yet reported, and remind the participant to bring back DC1 for V02. This telephone call will NOT be documented in the CRF.

**** Prior to these specified time-points, active surveillance will still occur during the established contacts (phone calls and visits).

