3. aggregated dose-level group, ie, low-dose arms pooled, or high-dose arms pooled
4. aggregated adjuvant type group, ie, AF03 arms pooled or AS03 arms pooled

The analyses by aggregated groups will also be conducted in overall population and by age group.

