5.2.3 Per-Protocol Analysis Set

Subset of the FAS. Participants presenting with at least one of the following conditions will be excluded from the PPAS:

- Participant did not meet all protocol-specified inclusion criteria or met at least one of the protocol-specified exclusion criteria
- Participant did not complete the protocol-defined vaccination schedule
- Participant received a study intervention other than the one that he / she was randomized to receive
- Preparation and / or administration of study intervention was not done as per-protocol
- Participant did not receive study intervention in the proper time window as defined in the protocol visits.
- Participant received a Category 2 or Category 3 therapy /medication / as stated in Section 6.5 of the Protocol
- Participant with positive test results in the neutralization test at baseline.

The above conditions leading to exclusion from the PPAS may be detailed and completed if necessary following the data review. In any case, if PPAS definition is modified, the PPAS definition will be finalized before the database lock and documented in an SAP update.

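### At D22 both cohorts have had one injection, yet SAP 5.1.1.4 summarizes D22 by 1-injection versus 2-injection and never pools the same dose-by-adjuvant formulation across cohorts

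*SAP*

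**What the plan says.** SAP 3.1 gives both cohorts the same start: "All participants will receive 1 injection of either one of the investigational study vaccine formulations or the placebo control at Day (D)01". Only Cohort 2 is injected again, at D22. The footnote to the Cohort 2 schedule (SAP 3.2, Table 3.2) fixes the order at that visit: "and BL0002, MC0002, and WB0002 samples will be collected at pre-VAC2".

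SAP 5.1.1.4 lists titer, fold-rise, 2-fold and 4-fold rise, and seroconversion. All include D22, and titer also includes D01. It then defines six main effects and says: "The primary endpoints above will also be summarized for the main effects". The third is injection schedule, with Cohort 1 vaccine arms as 1-injection (N=120) and adjuvanted Cohort 2 arms as 2-injection (N=240). No visit is excluded.

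Protocol 9.4.2.1 is narrower for its optional regressions: "Models evaluating antibody titers or rates at D36 as the outcome variable would include also an explanatory variable corresponding to the injection schedule". The SAP's optional model takes D22 for Cohort 1 and D36 for Cohort 2.

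On pooling, the dose main effect combines cohorts but mixes adjuvants, and the adjuvant main effect combines cohorts but mixes doses. The safety aggregates in SAP 5.1.1.2 follow the same pattern, for example "aggregated adjuvant type group, ie, AF03 arms pooled or AS03 arms pooled". They also pool the two placebo arms.

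Primary immunogenicity uses the PPAS-IAS, with confirmation on the FAS (SAP 5.2.5). One PPAS exclusion in SAP 5.2.3 is: "Participant did not complete the protocol-defined vaccination schedule".

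**The concern.** A D22 row labelled 2-injection describes people who have had one injection. Protocol 4.2 treats both the D22 and the D36 titers as informative for choosing the schedule, so a reader could take a D22 difference between these rows as evidence on that question. Any such difference can come only from chance, from the make-up of the two groups, or from who is left in the analysis set.

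The trial also exists to choose a formulation as well as a schedule. At D22, and for reactions between the two injections, Groups 1 and 6, 2 and 7, 3 and 8, 4 and 9, and 5 and 11 have had identical treatment. The plan has no column that puts each pair together, so the one-injection profile of a formulation is split over two arms.

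Finally, a Cohort 2 participant who misses injection 2 leaves the PPAS-IAS together with a valid D22 result obtained beforehand. Protocol 7.1.2 includes reactions to the first injection among the reasons for stopping. A Cohort 1 participant with the same reaction stays in.

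**Working it through.** **Inputs.** Arm sizes are from SAP 3.1 and Protocol Table 4.2. In adults 18-49, each arm has 20, or 60 for the AS03 arms of Cohort 2. In adults 50 and older, each arm has 10, or 30 for the AS03 arms of Cohort 2. The unadjuvanted arm has 20 younger adults only. The documents give no SD for log10 titer, so 0.5 is assumed, with a range of 0.3 to 0.7.

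**Reproducing the plan's group sizes.**
- 1-injection: 4 arms x (20 + 10) = 120, as stated.
- 2-injection: 2 AF03 arms x (20 + 10) + 2 AS03 arms x (60 + 30) = 60 + 180 = 240, as stated.

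**Make-up of the two schedule groups.** AS03 share: 60/120 = 50% against 180/240 = 75%. Adults 50 and older are one third of both groups, and the two dose levels are equally represented within each adjuvant in each cohort. Adjuvant is therefore the factor out of balance.

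**What the D22 rows would show with no schedule effect.** Let *a* and *b* be the mean log10 titers at D22 for AS03 and AF03.
- 1-injection mean = 0.50a + 0.50b
- 2-injection mean = 0.75a + 0.25b
- Difference = 0.25(a - b), so the GMT ratio is (AS03/AF03 ratio)^0.25

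For assumed adjuvant ratios of 1, 2, 3 and 4 this gives 1.00, 1.19, 1.32 and 1.41.

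**Gain from pooling a formulation over cohorts.** The comparison is with the larger single arm already tabulated.

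| Group | Cohort 1 | Cohort 2 | Pooled | Gain over larger arm |
|---|---|---|---|---|
| Each AF03 formulation | 30 | 30 | 60 | 2.0x |
| Placebo | 30 | 30 | 60 | 2.0x (immunogenicity only) |
| Each AS03 formulation | 30 | 90 | 120 | 1.33x |
| Each AS03 formulation, 50 and older | 10 | 30 | 40 | 1.33x |

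**Precision of a D22 GMT.** The 95% CI factor is 10^(t x SD/√n), with t on n - 1 degrees of freedom as in SAP section 5.

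| Formulation | n | SD 0.3 | SD 0.5 | SD 0.7 |
|---|---|---|---|---|
| AF03, one arm | 30 | 1.29 | 1.54 | 1.83 |
| AF03, pooled | 60 | 1.20 | 1.35 | 1.52 |
| AS03, Cohort 2 arm | 90 | 1.16 | 1.27 | 1.40 |
| AS03, pooled | 120 | 1.13 | 1.23 | 1.34 |

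**Events after injection 1, none observed.** The two-sided 95% Clopper-Pearson upper limit is 1 - 0.025^(1/n).
- AF03: 11.6% (n=30) to 6.0% (n=60)
- AS03: 4.0% (n=90) to 3.0% (n=120)
- AS03, 50 and older: 11.6% (n=30) to 8.8% (n=40)

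**The case against.** **The study tests nothing.** Protocol 9.1 says "All analyses will be descriptive; no hypotheses are planned to be tested", Protocol 9.2 says "No formal power calculation has been performed", and SAP 5.1.1.4 calls the main effects complementary. The sampling order is disclosed, and D22 rows by cohort could serve as a check that the cohorts were comparable before the second injection. This stands as a limit on the harm: there is no error rate to inflate. It does not rescue the label. As a comparability check, rows with 50% and 75% AS03 would mislead unless split by adjuvant.

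**The AS03 arms are already well covered.** A reader might infer that pooling is worth a fourfold sample, or that one-injection results are available only at n=30. The documents do not support that. Individual arms are summarized (Protocol 9.4.1), and safety is analyzed after each dose (SAP 5.2.2). Each Cohort 2 AS03 arm therefore already supplies a one-injection estimate at n=90. The ratio 120/30 = 4 holds only against the Cohort 1 arm and ignores that column. The doubling applies to AF03, to which Protocol 4.2 gives lower priority, and to placebo immunogenicity. Placebo safety is already pooled.

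**The FAS keeps the D22 values.** A reader might infer that the D22 results of Cohort 2 participants who miss injection 2 are lost to the analysis. They are not: the FAS requires one injection only (SAP 5.2.1), and SAP 5.2.5 repeats the immunogenicity analyses there. The exclusion affects the per-protocol tables alone. Safety uses the SafAS and is untouched.

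**Conclusion.** The point holds as a labelling and pooling fault in a descriptive plan. The D22 schedule rows cannot show a schedule effect. With AS03 at 50% and 75% of the two groups, they would instead show the fourth root of any AS03/AF03 ratio: 1.19 to 1.41 for assumed ratios of 2 to 4, and nothing if the adjuvants perform alike.

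The precision forgone is real but uneven. At an assumed log10 SD of 0.5, the D22 GMT factor would improve from 1.54 to 1.35 for AF03 and only from 1.27 to 1.23 for AS03. The group sizes and zero-event limits assume that planned enrollment is reached with complete data.

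The PPAS-IAS selection is secondary. The documents give no expected number of missed second injections, so its size cannot be stated.

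**What to change.** In SAP 5.1.1.4:
- Limit the injection-schedule main effect to D36 and later. The same AS03 imbalance persists there, so showing that summary within adjuvant as well would help.
- Add D22 summaries by formulation pooled across cohorts (Groups 1+6, 2+7, 3+8, 4+9 and 5+11), overall and by age group, in a set whose membership does not depend on receiving injection 2.

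In SAP 5.1.1.2, add the pooled formulation groups for reactions and AEs after injection 1 and, in Cohort 2, before injection 2. The pooled placebo group is already there.

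Keep the per-arm tables alongside. Schedule is unblinded, and 6 of the 30 in each Cohort 1 arm are sentinels enrolled earlier, so readers should be able to see whether the two arms of a pair agree.

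The cost is SAP wording and some extra table columns, with no new data. A partial database lock has already taken place (Protocol 9.5), and SAP 5.1.2.4 says the formulation is not being taken further. The change therefore serves the remaining analyses, the study reports and publication.

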The study will be conducted in adults 18 years of age and older. Clinical and epidemiological data from the COVID-19 pandemic have consistently indicated a higher risk of severe complications and death in older adults (35) (36). Therefore, it is considered of great relevance to generate data in the older adult population to inform schedule and formulation selection that will serve the general adult population, including those at particular risk of poor outcomes. A Sentinel Safety Cohort among younger adults is included to provide preliminary short-term safety data prior to enrollment of older adult participants. The study incorporates several measures to mitigate the theoretical risk of vaccine-associated ERD. These include a higher representation of the younger adult strata for the same reason, given that adults over 50 years of age have also been overrepresented in studies describing critical illness and death, although to a lesser degree than those older than 75 years (35). Therefore, the proposed design aims at generating data that will allow selection of the relevant formulations and injection schedule accounting for potential age

effects. Data for each formulation will be generated in both younger adults and older adults, allowing the evaluation of the consistency in the patterns of immune response for each formulation between the 2 age strata; additionally, aggregated “main” effects by age will be evaluable by comparing pooled older adult data (n=120 across vaccine formulations) and pooled younger adult data (n=240 across vaccine formulations with corresponding data in the older strata).

Evidence to date indicates that individuals with chronic medical conditions are at increased risk of severe outcomes associated with COVID-19 (37). The exclusion of individuals with chronic underlying conditions is considered an additional risk mitigation measure to address the theoretical phenomenon of immune enhancement. Clinical and epidemiological data indicates that the overrepresentation of older adults among those with critical or fatal COVID-19 illness is meaningfully ameliorated when stratified/controlled for the presence of chronic medical conditions (26). Exclusion of individuals with chronic medical conditions from this trial mitigates the potential (theoretical) risk of exacerbating the occurrence of critical or fatal outcomes as a result of study participation.

Rationale for Active Arms

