6.3 Measures to Minimize Bias: Randomization and Blinding

6.3.1 Randomization and Allocation Procedures

On the day of enrollment, participants who meet the eligibility criteria and sign the Informed Consent Form (ICF) will be stratified by 2 age groups (18-49 years and ≥ 50 years) and then be randomly assigned to receive 1 injection (Cohort 1) or 2 injections (Cohort 2) of CoV2 preS DTM investigational study vaccine or placebo. As shown in [Table 4.2](#), within each cohort:

- participants aged 18-49 years:
 - will be randomized to 6 groups to receive Antigen Formulation 1 (low-dose [5 μ g]) with either AF03 or AS03 adjuvant; Formulation 2 (high-dose [15 μ g]) with either AF03, AS03, or no adjuvant; or placebo (Note: unadjuvanted arm included in Cohort 2 only)
 - N = 20 participants in each group, except for AS03-adjuvanted groups in Cohort 2 with 60 participants in each group
- participants aged ≥ 50 years:
 - will be randomized to 5 groups to receive Antigen Formulation 1 (low-dose [5 μ g]) or Formulation 2 (high-dose [15 μ g]) each with either AF03 or AS03; or placebo
 - N = 10 participants in each group, except for AS03-adjuvanted groups in Cohort 2 with 30 participants in each group

The study will initially enroll 30 participants (6 within each dosing group from Cohort 1) 18-49 years of age, who will comprise the Sentinel Safety Cohort. Participants in this cohort will receive 1 injection of study intervention to which they were randomized, and safety and laboratory parameters up to D09 will be evaluated. Upon demonstration of acceptable safety, the remaining participants in Cohort 1 and all participants in Cohort 2 will be enrolled and randomized.

A subset of 87 participants in Cohort 2 (60 participants 18-49 years of age [18 per group in AS03-adjuvanted vaccines; 6 per group in all other study groups]) and 27 participants ≥ 50 years of age [9 per group in AS03-adjuvanted groups; 3 per group in all other study groups, with the exception of the unadjuvanted group for which there will be no older adults]), will be randomly assigned to a cellular-mediated immune (CMI) subset.

Site staff will connect to the Interactive Response Technology (IRT), enter the identification, security information, and confirm a minimal amount of data in response to IRT prompts. The IRT will then provide the group assignment and have the site staff confirm it. The full detailed

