4.4.5 Other Derived Variables

4.4.5.1 Age for Demographics

The quantitative descriptive statistics (e.g., Mean, SD, Max, Min, Median, Q1 and Q3) of age in demographics summary table(s) is based on the age in year collected in eCRF.

Age group

The age in year collected in eCRF will be used for demographics summary and age sub-groups definition. The age groups of a participant used in the study are as follows:

“18 to 49 years”, “Over 50 years” and “Over 60 years”

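### Two SAP age definitions are wrong as written: the ≥50 main-effect category is described as the 18-49 arms, and the derived age groups leave out participants aged exactly 50

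*SAP*

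**What the plan says.** **The age main effect.** SAP 5.1.1.4 pools vaccine arms for six complementary main-effect comparisons of the primary immunogenicity endpoints. The first is age, 18-49 against ≥50. The younger category is described as "N=240) includes all vaccine arms except high dose no adjuvant arm aged 18-49 years old". The older category carries the label ≥50 years and is then described as "N=120) includes all vaccine arms aged 18-49 years old".

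**The derived age groups.** SAP 4.4.5.1 states that age in years from the eCRF serves both the demographics summary and the definition of age sub-groups. It lists the groups as "18 to 49 years”, “Over 50 years” and “Over 60 years". Neither document gives any other rule for deriving age groups from recorded age.

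**The design.** Protocol 6.3.1 says that eligible participants "will be stratified by 2 age groups (18-49 years and ≥ 50 years". SAP 3.1 and 5.5 describe the older stratum as 50 years or older, and the regression covariate in SAP 5.1.1.4 is coded 18-49 and ≥50. Protocol 4.2 describes the age comparison as using "pooled older adult data (n=120 across vaccine formulations", and Protocol 9.2 repeats 120 for ≥50.

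**The concern.** Both passages tell a programmer which participants go into which column, so they are operative definitions and not background text. In 5.1.1.4 the description of the older category contradicts its own label and its own N. In 4.4.5.1 the cut-off leaves a gap between 49 and 'over 50' that the randomisation strata do not have.

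Age group runs through much of the output. The primary safety objective is stated by age group (SAP 2.1). SAP 5.1.1.2 describes safety for each age and vaccine group, and the aggregated safety groups are also shown by age. SAP 5.1.1.4 asks for primary immunogenicity overall and by age. SAP 5.1.3 does the same for the binding-to-neutralizing antibody ratio, antibody persistence and the Th1/Th2 ratios.

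If 4.4.5.1 were coded literally, a 50-year-old would appear in the overall tables and in the ≥50 level of the regression but in no by-age table. The by-age columns would then not add up to the overall column.

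**Working it through.** **Inputs.** Planned arm sizes come from Protocol Table 4.2. Protocol 6.3.1 gives the same sizes in words: for 18-49, "N = 20 participants in each group, except for AS03-adjuvanted groups in Cohort 2 with 60 participants in each group"; for ≥50, "N = 10 participants in each group, except for AS03-adjuvanted groups in Cohort 2 with 30 participants in each group". The older stratum has no unadjuvanted arm. Placebo groups 5 and 11 are left out because the main effects pool vaccine arms only.

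| Vaccine groups | 18-49 | ≥50 |
|---|---|---|
| Cohort 1, groups 1-4 | 4 × 20 = 80 | 4 × 10 = 40 |
| Cohort 2, groups 6, 7, 8, 9 | 20 + 60 + 20 + 60 = 160 | 10 + 30 + 10 + 30 = 80 |
| Cohort 2, group 10 (unadjuvanted) | 20 | none |
| All vaccine arms | 260 | 120 |
| Without group 10 | 240 | 120 |

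**Step 1: the younger category.** 260 − 20 = 240, which reproduces the SAP's N=240.

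**Step 2: the older category as written.** All vaccine arms aged 18-49 give 260, or 240 if group 10 is dropped. Neither is 120. Taken literally, the category labelled ≥50 would hold the same 240 people as the comparison category plus the 20 in group 10, and no older adult.

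**Step 3: the older category with the age corrected.** All vaccine arms aged ≥50 give 40 + 80 = 120. This matches the SAP's N=120 and the 120 in Protocol 4.2 and 9.2.

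**Step 4: the other main effects.** Summing both strata gives:
- low dose (groups 1, 2, 6, 7): 30 + 30 + 30 + 90 = 180
- high dose with adjuvant (3, 4, 8, 9): 30 + 30 + 30 + 90 = 180
- one injection (1-4): 4 × 30 = 120
- two injections (6-9): 30 + 90 + 30 + 90 = 240
- AS03 (2, 4, 7, 9): 30 + 30 + 90 + 90 = 240
- AF03 (1, 3, 6, 8): 4 × 30 = 120
- unadjuvanted high dose (10): 20

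All agree with the SAP. The ≥50 category is the only one whose description does not give its N.

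**Step 5: the derived groups.** Applying the labels in SAP 4.4.5.1 literally to ages around the boundaries:

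| Age | Group under SAP 4.4.5.1 | Randomisation stratum |
|---|---|---|
| 49 | 18 to 49 | 18-49 |
| 50 | none | ≥50 |
| 51 | over 50 | ≥50 |
| 60 | over 50 | ≥50 |
| 61 | over 50 and over 60 | ≥50 |

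Only age 50 loses its group. Someone aged 61 is in two groups because the over-60 group lies inside the over-50 group.

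**Step 6: scale.** Eight of the ten older arms (groups 1-6, 8 and 11) have 10 planned participants, so each 50-year-old missing from such an arm removes 1/10 = 10% of it. How many such participants there are cannot be derived: neither document gives an age distribution within the older stratum.

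**The case against.** The strongest reply is that both slips correct themselves. In 5.1.1.4 the label says ≥50, the N is 120, and only the ≥50 arms produce 120; the regression covariate in the same section also says ≥50. A programmer could not satisfy the label and the N by pooling 18-49 arms. In 4.4.5.1 the adjacent group stops at 49 and every design passage uses ≥50, so 'over 50' is most naturally loose shorthand for 50 and over. Even on the strict reading, 50-year-olds stay in every overall-population table. This stands as an account of what was intended. It does not make the definitions correct, and for the derived groups no text says that 'over 50' includes 50.

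A reader might infer more than the documents support, in three ways:

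- **That the age contrast will be young against young and distort formulation choice.** The intent is too clear for the first part to be a realistic expectation. On the second, SAP 5.4 limits dose selection to the first interim and reports that a partial database lock has already been done. SAP 5.1.2.4 and 5.7 add that the formulation is no longer being investigated. Correcting this text would not alter formulation selection.
- **That the overlap between the over-50 and over-60 groups is an error.** A nested older subgroup is ordinary practice, and nothing in 4.4.5.1 requires the three groups to partition the sample. The SAP leaves the nesting and the boundary unstated, which calls for a clarification.
- **That a definite number of participants will be lost.** Any headcount would need an assumed share aged exactly 50, and the documents offer no basis for one.

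**Conclusion.** The point holds as a correction of two operative definitions. The description of the ≥50 category in SAP 5.1.1.4 is wrong: it names arms that total 260 (240 without the unadjuvanted arm) where the stated and intended N is 120. The derived groups in SAP 4.4.5.1, read literally, leave age 50 unassigned and so disagree with the randomisation stratum and with the rest of the SAP.

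The consequence is minor. No planned N changes, no hypothesis is tested, and the overall-population tables are unaffected. What is at stake is whether the by-age summaries hold the participants they should. For the derived groups this depends on the strict reading of 'over' and on how many participants are exactly 50, so the effect cannot be sized.

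**What to change.** 1. In SAP 5.1.1.4, main effect 1, change the age in the description of the ≥50 category from 18-49 to ≥50 years. Keep N=120.
2. In SAP 4.4.5.1, replace the over-50 label with ≥50 years, so that the two main groups are those used for randomisation.
3. If the over-60 group is kept, label it as a subset of ≥50 and have the sponsor state whether it means >60 or ≥60. The documents do not settle that boundary.

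The cost is two SAP lines, with no new data and no change to design or sample size. If by-age outputs have already been programmed, confirm that the code uses ≥50 and that the 18-49 and ≥50 counts add up to the overall count in each table.
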